4.1.2.2 Concomitant medication date imputation

The imputation of the start date of concomitant medication will follow the same conventions as for AE date. Partial concomitant medication end dates will not be imputed.

4.1.2.3 Incomplete date of initial diagnosis of cancer, date of first recurrence/progression and date of most recent recurrence

Missing day is defaulted to the 15th of the month and missing month and day is defaulted to 01-Jan.

If the imputed first recurrence date is after recent recurrence date, use the recent recurrence date as first recurrence.

If the imputed recent recurrence date is before the first recurrence, use the first recurrence date as the most recent recurrence. If both first recurrence and recent recurrence are imputed and the imputed first recurrence is after the recent recurrence, then use the imputed recent recurrence as the first recurrence date.

4.1.2.4 Incomplete date for anti-neoplastic therapies

Prior therapies

Start date:

The same rule which is applied to the imputation of AE/concomitant medication start date will be used with the exception that for scenario (B) will be replaced to be 'start date of treatment -1'.

End date:

Imputed date = min (start date of study treatment, last day of the month), if day is missing;

Imputed date = min (start date of study treatment, 31DEC), if month and day are missing.

If the end date is not missing and the imputed start date is after the end date, use the end date as the imputed start date.

If both the start date and the end date are imputed and if the imputed start date is after the imputed end date, use the imputed end date as the imputation for the start date.

Post therapies

Start date:

Imputed date = max (last date of study treatment + 1, first day of the month), if day is missing;

Imputed date = max (last date of study treatment + 1, 01JAN), if day and month are missing.

End date: No imputation

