5.2 Inclusion criteria

Patients eligible for inclusion in this study have to meet all of the following criteria:

1. Histologically or cytologically confirmed diagnosis of NSCLC, that carries an ALK rearrangement defined as positive using the FDA approved Vysis ALK Break Apart FISH Probe Kit (Abbott Molecular Inc.) test and scoring algorithm (including positivity criteria) or positive as assessed by the CFDA approved immunohistochemistry (IHC) test (Ventana Medical Systems, Inc) using rabbit monoclonal primary antibody assay (D5F3) and associated scoring algorithm. If documentation of ALK rearrangement is not available as described above, a test to confirm ALK rearrangement must be performed using an archival tumor obtained at or since the time of diagnosis or a new tumor biopsy obtained prior to the first LDK378 dose. The test will be performed at a Novartis designated central laboratory (by IHC test using rabbit monoclonal primary antibody assay (D5F3), Ventana Medical Systems, Inc). Patients must wait for the result of the ALK rearrangement status before initiating treatment with LDK378.
2. Age 18 years or older at the time of informed consent.

3. Patients must have stage IIIB or IV NSCLC at the time of study entry and have had progressive disease during or after crizotinib treatment whether or not previously treated with cytotoxic chemotherapy. If treated with chemotherapy, maximum 2 lines are allowed.
 - Patients must have progressive disease at study entry. Patients are not eligible if crizotinib was discontinued due to toxicity.
 - Patients must have received their last dose of crizotinib \geq 1 week prior to the first dose of LDK378 and recovered from crizotinib toxicities (as defined in inclusion criteria #4)
 - Prior targeted therapies will not count as a line of cytotoxic chemotherapy (i.e. patients may have received prior treatment with these drugs excluding ALK-inhibitors – See exclusion criteria # 6).
 - (Neo-) adjuvant cytotoxic chemotherapy will count as one prior line of treatment if relapse occurred within 12 months from the end of the adjuvant cytotoxic chemotherapy

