Prior anti-neoplastic (anti-cancer) therapy will be listed in three separate categories: 1. medications, 2. radiotherapy, and 3. surgery.

The number and percentage of patients who received any prior anti-neoplastic medications, prior anti-neoplastic radiotherapy or prior anti-neoplastic surgery will be summarized.

All patients must have received crizotinib for inclusion in the study; reason for crizotinib discontinuation, best response on crizotinib, duration of best response, and time from start of last crizotinib treatment to progression (date of progression on crizotinib - start date of last crizotinib + 1) will be summarized.

Prior anti-neoplastic medications will be summarized by chemotherapy (medication) setting, other therapy (medication) setting, number of prior regimens of chemotherapy. Prior antineoplastic medications will also be summarized by Anatomical Therapeutic Chemical (ATC) class and PT using the latest WHO drug dictionary prior to database lock.

The summary of prior anti-neoplastic radiotherapy will include a summary of radiotherapy locations and settings at last radiotherapy.

The summary of prior anti-neoplastic surgery will include the time between the last surgery to start of treatment, procedure at last surgery and residual disease at last surgery.

Screening phase disposition

Patients who sign an informed consent but fail to be started on treatment for any reason will be considered a screening failure. These patients are not treated with study drug. Frequency counts and percentages will be tabulated for all patients as follows:

- Number (%) of patients who completed screening phase (based on the presence of study phase completion date/ "subject status" is checked as "completed" and the 'Next phase entered' is 'Treatment' or 'Treatment run-in' in the 'Screening Phase Disposition' page);
- Number (%) of patients who discontinued during screening phase (based on the presence of date of discontinuation and discontinuation / "subject status" reason entered and 'Will the subject continue into the next phase of the trial' is 'No' in the 'Screening Phase Disposition' page);

- Reasons for screening phase discontinuation (based on reasons recorded in Screening Phase Disposition' page)

All screen failure patients with reasons for screen failure will be listed and summarized by criteria.

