4.1.2.1 AE date imputation

Date imputation is the creation of a new, complete date from a partial one according to an agreed and acceptable algorithm. Missing date for AE will be handled according to rules specified below. A partial date is simply an incomplete date e.g. DDOCT2001: the days are missing from this DDMMYY date.

Partial AE start dates, if left partial, would ultimately mean the following

It would not be possible to place the AE in time.

Therefore the treatment/dosage at the time of the event would be unknown.

Therefore the event could not be reported/summarized appropriately – if at all.

Therefore it is important to perform date imputation to ensure that as many data events are represented as correctly as possible. Of course partial and/or missing dates should *also* be caught as edit checks and passed back to the investigator for resolution.

There **will be no** attempt to impute the following:

- **Missing** AE start dates
- AE start dates **missing the year**
- Partial/missing AE **end dates**

The following [Table 4-1](#) explains the abbreviations used.

Table 4-1 AE/treatment date abbreviations

	Day	Month	Year
Partial Adverse Event Start Date	<not used>	AEM	AEY
Treatment Start Date (TRTSTD)	<not used>	TRTM	TRTY

The following matrix [Table 4-2](#) describes the possible combinations and their associated imputations. In the light grey boxes the upper text indicates the imputation and the lower text the relationship of the AE start date to the treatment start date (TRTSTD).

Table 4-2 AE partial date imputation algorithm

	AEM MISSING	AEM < TRTM	AEM = TRTM	AEM > TRTM
AEY MISSING	NC Uncertain	NC Uncertain	NC Uncertain	NC Uncertain
AEY < TRTY	(D) Before TRTSTD	(C) Before TRTSTD	(C) Before TRTSTD	(C) Before TRTSTD
AEY = TRTY	(B) Uncertain	(C) Before TRTSTD	(B) Uncertain	(A) After TRTSTD
AEY > TRTY	(E) After TRTSTD	(A) After TRTSTD	(A) After TRTSTD	(A) After TRTSTD

The following [Table 4-3](#) is the legend to the above table.

Table 4-3 AE/treatment date relationship and imputation legend

Relationship	
Before TRTSTD	Indicates AE start date prior to Treatment Start Date
After TRTSTD	Indicates AE start date after Treatment Start Date
Uncertain	Insufficient to determine the relationship of AE start date to Treatment Start Date
Imputation Calculation	
NC / Blank	No convention/imputation
(A)	01MONYYYY
(B)	TRTSTD+1
(C)	15MONYYYY
(D)	01JULYYYY
(E)	01JANYYYY

The following [Table 4-4](#) gives a few examples.

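### SAP date rules can make time to progression on crizotinib one day, zero or negative for some partial start dates, and time since last relapse negative for some partial relapse dates (minor, descriptive tables only)

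*SAP*

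**What the plan says.** **Start of prior therapy.** SAP 4.1.2.4 takes over the adverse-event algorithm of SAP 4.1.2.1 (Tables 4-2 and 4-3), "with the exception that for scenario (B) will be replaced to be" first dose minus 1 day. Scenario (B) is the cell whose legend reads "Insufficient to determine the relationship of AE start date to Treatment Start Date". It covers a partial date in the first-dose year whose month is missing or is the first-dose month. An earlier known month gets the 15th (C), and an earlier year with no month gets 01JUL (D). A back-stop follows for a known end date: if "the imputed start date is after the end date, use the end date as the imputed start date".

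**End of prior therapy.** "Imputed date = min (start date of study treatment, last day of the month), if day is missing"; with the month also missing, 31DEC replaces the last day of the month.

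**Use.** SAP 3.2.2 plans a summary of "time from start of last crizotinib treatment to progression", defined as progression date minus start date plus 1. It also summarizes time since the most recent relapse or progression.

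**Eligibility.** Protocol 5.2, criterion 3: "Patients must have received their last dose of crizotinib" at least 1 week before first LDK378. Progression may be during or after crizotinib.

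**Recurrence dates.** SAP 4.1.2.3: "Missing day is defaulted to the 15th of the month and missing month and day is defaulted to" 01-Jan. There is no upper bound at first dose. SAP 4.1.2.7, for progression on crizotinib, does bound the date at the start of LDK378 in the branches where crizotinib ended in or before the progression month or year.

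**The concern.** For an adverse event of uncertain timing, placing it just after first dose is a cautious choice. Carried over to prior therapy as the day before first dose, the rule takes the latest conceivable start and so the shortest conceivable exposure. For crizotinib that day lies inside the required washout. The back-stop keeps the start from passing the stop date, but nothing keeps it from passing the progression date. SAP 4.1.2.7 itself provides for crizotinib ending after progression.

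At stake is the baseline description of a population defined by crizotinib failure: how long patients benefited before, and how recently they progressed. Scenario (B) can plausibly occur. Protocol 1.1.3 says these cancers typically progress in under a year and cites a median PFS of 7.7 months on crizotinib, so a patient starting LDK378 late in a year could have started crizotinib that same year. With about 100 patients, a few zero or negative values would show in the minimum and pull the mean.

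**Working it through.** **The plan's own examples.** Coding Tables 4-2 and 4-3 reproduces all seven rows of SAP Table 4-4 (treatment start 20OCT2001). The midpoint example in SAP 4.1.2.7 (27 to 30 June 2012) gives 29 June 2012; the SAP prints 2013, a slip in the year.

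**Scenario (B), complete stop date.** Let L be first LDK378 dose, E the crizotinib stop date and P the progression date.

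- Imputed start = L − 1.
- The washout gives E ≤ L − 7, so L − 1 > E and the back-stop always sets start = E.
- Time to progression = P − E + 1. The true start has dropped out.

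Enumeration gave no exception in 2,861,782 combinations (L on every day of 2014, E from 7 to 90 days earlier in 2014, P from 60 days before E up to L).

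Example: L = 20OCT2014, start recorded as 2014, E = 06OCT2014. The imputed start is 19OCT, reset to 06OCT. The last column assumes a true start of 01FEB2014.

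| Progression | Result (days) | Assumed truth (days) |
|---|---|---|
| 06OCT (on stop date) | 1 | 248 |
| 05OCT | 0 | 247 |
| 26SEP | −9 | 238 |
| 15OCT (after stop) | 10 | 257 |

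**Partial stop date as well.** With the same L and start 2014, a stop of OCT2014 is imputed as min(20OCT, 31OCT) = 20OCT, which implies no washout. The start stays at 19OCT, and progression on 01OCT gives −18 + 1 = −17 days. A stop of 2014 with progression on 01SEP gives −48 + 1 = −47.

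**Scenario (D).** Start 2013, stop 20MAY2013, progression 10MAY2013: 01JUL2013 is reset to 20MAY2013, giving −10 + 1 = −9 days (126 if the true start was 05JAN2013).

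**Where the rule behaves acceptably.** With L = 20OCT2014 and stop and progression on 06OCT2014, start FEB2014 (scenario C) gives 234 days against an assumed 248. Start 2013 (scenario D) gives 463 against an assumed 613 for a start on 01FEB2013.

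**Relapse date, day missing.** The reference date is taken as first dose, in line with SAP 3.1.1.5 (assumption). If relapse is in the first-dose month, the imputed 15th falls after first dose whenever LDK378 starts on days 1 to 14: 14 × 12 = 168 of 365 start days (46%), down to −14 days.

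For first dose on day d of the month and a gap of k days, a negative value needs d ≤ 14 and k ≤ d − 1. Assuming start days spread evenly over a year and gaps uniform within each window:

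- Gap 1–28 days: (0 + 1 + … + 13) × 12 = 1,092; 1,092 / (365 × 28) = 10.7%.
- Gap 1–56 days: 1,092 / (365 × 56) = 5.3%.
- Gap 7–42 days: (1 + 2 + … + 7) × 12 = 336; 336 / (365 × 36) = 2.6%.

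**One event, two dates.** Suppose progression is recorded only as 2014, crizotinib stopped on 01-Aug and LDK378 began on 20-Oct. SAP 4.1.2.7 gives the midpoint of 01-Aug and 31-Dec, 16-Oct-2014. If the same event is also the most recent recurrence, SAP 4.1.2.3 gives 01-Jan-2014, 288 days earlier.

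**The case against.** **Reach.** A reader might infer that any partial crizotinib date ruins the interval. The documents do not support that. Scenario (C), and (D) when crizotinib ran past 01JUL, usually give plausible values. Even within (B), progression after stopping, which the protocol allows, gives a positive though too short result. This objection stands.

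**Impossible dates.** It is tempting to call the imputed start impossible. First dose minus 1 day is incompatible with the washout, but with a complete stop date it is only an intermediate value. The start finally used is the stop date, which is implausible rather than impossible. Only a zero or negative interval is impossible, since progression on crizotinib cannot precede its start.

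**Queries.** SAP 4.1.2.1 wants partial dates returned to the investigator, and Protocol 9.4 provides for queries on missing values. That should keep the numbers small, but it does not correct the rule for dates that stay partial.

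**Consequence.** ORR, DOR, PFS, OS, PK and safety do not use these dates, and the visible text plans no response analysis by crizotinib duration. This stands and settles the grade.

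**Relapse share and double dating.** The washout limits the last crizotinib dose, not the relapse date, so no single window is favoured and only a range can be given. The documents also do not say that the most recent relapse and the crizotinib progression are the same event; the two-date conflict holds only where they are.

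**Conclusion.** Wrong as written, but minor. In scenario (B), and in (D) when crizotinib ended before 01JUL of its start year, the planned interval with a complete stop date no longer measures time on crizotinib to progression. It reports the gap between stopping and progressing, plus 1. It is zero or negative for every such patient who continued crizotinib past progression. Time since most recent relapse can be negative by up to 14 days. That affects about 3% to 11% of day-missing relapse dates under assumed gaps of 7–42, 1–56 or 1–28 days, with first dose as reference.

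The documents do not say how many dates are partial, so the effect on the tables cannot be sized; it is probably small. Nor do they support reading this as a threat to the response rate or any other efficacy result. What suffers is the baseline description against which that rate is read.

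**What to change.** **SAP 4.1.2.4, prior-therapy start.** In scenario (B), and in (D) when 01JUL falls after the end date, impute the midpoint between two bounds:

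- lower: the earliest date compatible with the known part (01JAN, or the first of the month if the month is known);
- upper: the earliest of therapy end date, progression date (crizotinib only, where the SAP shows such a date is collected) and first dose.

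The aim is that start never exceeds end or progression, so apply the same bound in (D) if 01JUL falls after progression while crizotinib continued. In the example, stop 06OCT2014 with progression on 06OCT, 26SEP and 15OCT then gives 140, 135 and 149 days instead of 1, −9 and 10. The midpoint is a convention and will not recover the truth (248, 238 and 257 under the assumed start), but it cannot give a zero or negative interval when the recorded dates are consistent.

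**SAP 4.1.2.3.** Cap imputed recurrence dates at the start date of LDK378, matching the cap in 4.1.2.7. Where the most recent recurrence is the recorded crizotinib progression, use the 4.1.2.7 date for both. With first dose 03OCT2014 and relapse OCT2014, the value moves from −12 days to 0.

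**Cost.** Two SAP sentences and a change to the date macro; no new data. SAP 1.1 says the methods are similar to those of the primary report, so a footnote should mark any baseline value that changes from that report.

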4.1.2.5 Incomplete assessment dates for tumor assessment

All investigation dates (e.g. X-ray, CT scan) must be completed with day, month and year.

If one or more investigation dates are incomplete but other investigation dates are available, the incomplete date(s) are not considered for calculation of the assessment date and assessment date is calculated as the latest of all investigation dates (e.g. X-ray, CT-scan) if the overall lesion response at that assessment is CR/PR/SD/UNK. Otherwise, if overall lesion response is PD, the assessment date is calculated as the earliest date of all investigation dates at that evaluation number. If all measurement dates have no day recorded, the 1st of the month is used.

If the month is not completed, for any of the investigations, the respective assessment will be considered to be at the date which is exactly between the previous and the following assessment. If both a previous and following assessments are not available, this assessment will not be used for any calculations.

4.1.2.6 Incomplete date for death or last contact

All dates must be completed with day, month and year.

If the day or month is missing, death will be imputed to the maximum of the full (non-imputed) last contact date (excluding the date of death) and the following:

- Missing day: 15th day of the month and year of death
- Missing day and month: July 1st of the year of death

If the day is missing from the date of last contact it will be imputed to 15th day of the month and year of last contact only if derived from the survival page.

4.1.2.7 Incomplete dates for disease progression on Crizotinib prior to the start of study drug.

If day of progression associated with the 'Prior Antineoplastic Therapy – Crizotinib' page is missing then the imputed PD date is:

= min (midpoint between the end date of the prior crizotinib medication and the end of the month, start date of LDK), if end date of prior crizotinib medication is in the same month as the PD date.

= min (15th of the month of the PD date, start date of LDK), if end date of prior crizotinib medication is in a month prior to the PD date.

= 15th of the month of the PD date, if end date of crizotinib medication is in a month after the PD date.

If both day and month of progression associated with the 'Prior Antineoplastic Therapy – Crizotinib' page is missing then the imputed PD date is:

= min (midpoint between the end date of the prior crizotinib medication and the end of the year, start date of LDK) if end date of prior crizotinib medication is in same year as the PD date

= min (July 1 of the year of the PD date, start date of LDK), if end date of prior crizotinib medication is in a year prior to the PD date.

= July 1 of the year of the PD date, if end date of prior crizotinib medication is in a year after the PD date.

Completely missing PD dates will not be imputed. For the midpoint calculation, if odd days in between (e.g last dose of crizotinib is 27 June 2012, and end of the month is 30 June 2012), then use the next day from the midpoint calculation (e.g midpoint is 29 June 2013).

4.1.2.8 Incomplete dates for last dose of study drug

Scenario 1

If the last date of study drug is after the cut-off date or is completely missing and there is no end of treatment eCRF page and no death date the patient should be considered to be on-going and use the cutoff date for the analysis as the last dosing date

Scenario 2

If the last date of study drug is completely or partially missing and there is EITHER an end of treatment eCRF page OR a death date available then imputed last dose date:

- = 31DECYYYY, if only Year is available and Year < Year of min (EOT date, death date)
- = Last day of the month, if both Year and Month are available and Year = Year of min (EOT date, death date) and Month < the month of min (EOT date, death date)
- = min (EOT date, death date), for all other cases

The imputed date will be compared with start date of study drug.

If the imputed date < start date of study drug, then last date of study drug is set to start date of study drug;

Otherwise, use the imputed date.

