3.2.9 Safety evaluation

All safety analyses will be performed based on the Safety Set.

Grouping for the analyses

Safety summaries will include data from the following three mutually exclusive segments:

- Pre-treatment period: from day of patient's informed consent to the day before first dose of study treatment.
- On-treatment period:
 - For discontinued patients, from day of first dose of study drug to 30 days after last dose of study drug
 - For ongoing patients, from day of first dose of study drug to the data cut-off date
- Post-treatment period: starting at day 31 after last dose of study drug

The safety summary tables will include only assessments during the on-treatment period, unless otherwise specified. For select items, shift tables or change from baseline summaries generated

for laboratory, ECG, vital signs and change score generation may use data from pre-treatment period for baseline calculations.

All data, regardless of observation period, will be listed and assessments collected in pre-treatment and post-treatment period will be flagged in all the listings.

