4.1.2 Handling of missing or partial dates

For patients not known to have died prior to the cut-off date:

- All events with start date before or on the cut-off date, and with end date missing or after the cut-off date or after the date of withdrawal of informed consent will be reported as “continuing”.
- This approach applies, in particular, to AEs and concomitant medication report. For these events, the end date will not be imputed and therefore will not appear in the listings.

For patients known to have died prior to or on the cut-off date:

- All events with start date before or on the cut-off date, and with end date missing or after the cut-off date or after the date of withdrawal of informed consent will have the end date imputed to the death date.
- This approach applies, in particular, to AEs and concomitant medication report. For these events, the imputed end date will not appear in the listings.

If imputation of an end date is required for a specific analysis (e.g. for a dose administration record with missing end date or last date of study treatment after the cut-off date), the end date will be imputed to the min (cut-off date, death date, withdrawal of informed consent date) for the purpose of calculating duration of exposure to study drug and dose intensity. The imputed date will be displayed and flagged in the listings.

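### SAP 4.1.2.8 has no branch for a last dose whose known month lies in a year before the EOT or death date, and SAP 4.1.2 conflicts with it for patients who have stopped treatment

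*SAP*

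**What the plan says.** SAP 4.1.2.8, Scenario 2, covers a last-dose date that is "completely or partially missing and there is EITHER an end of treatment eCRF page OR a death date available". It has three branches:

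- Year only: "31DECYYYY, if only Year is available and Year < Year of min (EOT date, death date".
- Year and month: "Last day of the month, if both Year and Month are available and Year = Year of min (EOT date, death date", and the month must also be earlier than the EOT or death month.
- Otherwise: "min (EOT date, death date), for all other cases".

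The result is then floored at the first dose date. Cut-off is used only in Scenario 1, which requires that there be no EOT page and no death date.

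The last-dose date closes the on-treatment period in SAP 3.2.9: "For discontinued patients, from day of first dose of study drug to 30 days after last dose of study drug". It also sets the duration of exposure in SAP 3.1.1.3 (last date minus first date plus 1).

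SAP 4.1.2 has a second, general rule. It gives as its example an imputation needed "for a dose administration record with missing end date or last date of study treatment after the cut-off date", and says that "the end date will be imputed to the min (cut-off date, death date, withdrawal of informed consent date". The EOT date is not among the dates compared. The rule states its own scope, which is narrow: "for the purpose of calculating duration of exposure to study drug and dose intensity".

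**The concern.** In 4.1.2.8 the more complete record gets the worse answer. When the years differ, knowing the month as well as the year moves the imputed date past the recorded month, while knowing the year alone keeps it inside the recorded year. The year-only branch already handles an earlier year, so its absence from the year-and-month branch looks like an oversight.

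In 4.1.2 and 4.1.2.8, two sections address the same datum, because SAP 3.1.1.2 takes the last dose from the dosing records. They give different dates for a patient who has stopped, and the SAP does not say which prevails.

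Safety and tolerability is a primary objective. A last-dose date set too late under 4.1.2.8 can move a post-treatment event or death into the on-treatment tables and lengthen exposure. The 4.1.2 rule can lengthen exposure and alter dose intensity.

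**Working it through.** The documents give no figure that depends on these rules, so there is none to reproduce. All patient dates and cut-off dates below are assumed, to show how the rules behave.

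**1. The missing branch.** Take EOT on 20JAN2016 with no death date, and apply Scenario 2 as written. The last row is a control with EOT in the same year.

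| Recorded last dose | EOT | Branch met | Imputed | Latest date the record allows | Excess (days) |
|---|---|---|---|---|---|
| 2015 | 20JAN2016 | year only | 31DEC2015 | 31DEC2015 | 0 |
| NOV2015 | 20JAN2016 | catch-all | 20JAN2016 | 30NOV2015 | 51 |
| OCT2015 | 20JAN2016 | catch-all | 20JAN2016 | 31OCT2015 | 81 |
| NOV2015 | 20DEC2015 | end of month | 30NOV2015 | 30NOV2015 | 0 |

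The excess passes one-for-one into exposure and the safety window. For the NOV2015 record with first dose 01MAR2015, exposure is 326 days instead of 275 (326 − 275 = 51). The window closes on 19FEB2016 instead of 30DEC2015. The 51- and 81-day rows need an EOT visit well off schedule.

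**2. How large the excess can be.** Excess = EOT date − end of the recorded month. The true last dose is no later than the end of that month, so the excess cannot exceed the gap from last dose to EOT.

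- EOT on schedule (within 7 days of last dose, SAP 2.4): excess ≤ 7 days. The limit is reached with last dose 31DEC and EOT 07JAN. Only last doses from 25 to 31 December can cross the year.
- EOT after a dose hold: SAP 3.1.1.2 defines the last administration as the last non-zero dose, and Protocol 6.2.2 refers to holds of 28 consecutive days. Then 28 + 7 = 35 days. Protocol 6.2.2 allows longer holds where the investigator sees continuing benefit, so 35 is a typical figure and not a ceiling.
- Death date only: the rule sets no limit. For example, with last dose NOV2014, no EOT page and death on 20MAR2015, the excess is 31 + 31 + 28 + 20 = 110 days from 30NOV2014. The window should have closed by 30DEC2014, but the death is counted as on-treatment.

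**3. SAP 4.1.2 against 4.1.2.8.** Take first dose 01MAR2015, EOT page dated 20JUN2015, patient alive with consent not withdrawn, dosing end date missing. Under 4.1.2.8 the last dose is 20JUN2015, so exposure = 112 days. Under 4.1.2 read literally, exposure runs to cut-off:

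| Assumed cut-off | Exposure under 4.1.2 | Difference from 112 |
|---|---|---|
| 29SEP2015 | 213 | +101 |
| 20DEC2015 | 295 | +183 |
| 19JUN2016 | 477 | +365 |
| 19DEC2016 | 660 | +548 |

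**4. Dose intensity.** Suppose this patient took 750 mg for 60 days and 600 mg thereafter. To EOT, relative dose intensity is (60 × 750 + 52 × 600) / (112 × 750) = 76,200 / 84,000 = 90.7%. At the 29SEP2015 cut-off it becomes 136,800 / 159,750 = 85.6% if dosing is carried forward at 600 mg, or 76,200 / 159,750 = 47.7% if cumulative dose is left at its EOT value. The direction here is down, and the size depends on a choice the SAP does not state.

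**The case against.** The case for leaving this alone has four parts.

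- **The realistic error is small.** The EOT visit is due within 7 days, and Protocol 7.1.5 requires an End of Treatment Phase Disposition page when treatment stops. The 110-day example needs that page to be missing. Missing values are also queried before lock (Protocol 9.4). This stands, and it is why the point is minor.
- **A modestly late window has little to collect.** Adverse events are followed for at least 30 days after last dose (Protocol 7.1.7.1), and later serious events are reported only if suspected to be related (Protocol 8.2.2). All deaths are tabulated alongside on-treatment deaths (SAP 3.2.9.1). Any misclassification would overstate on-treatment toxicity and not hide it. This also stands.
- **The two sections can be read together.** On this reading, 4.1.2 is a general lead-in for patients still on treatment and 4.1.2.8 is the specific rule for those who have stopped. That is reasonable, but the SAP does not say so, and 4.1.2 expressly names dosing records, exposure and dose intensity. The conflict remains open.
- **4.1.2 does not touch the safety window.** A reader might infer that both rules push post-treatment events into the safety tables. The text does not support this: 4.1.2 confines its imputation to exposure and dose intensity. Only the 4.1.2.8 gap can move the window.

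A reader might also infer that stopped patients are in fact given many extra months of exposure. With 66 of 103 treated patients already off treatment at 29-Sep-2015 (Protocol, Amendment 3 rationale), and a cut-off assumed at the SAP date of 13-Feb-2017, the literal 4.1.2 rule would add 503 days, about 16.5 months, for a patient whose EOT date was 29-Sep-2015. That needs a missing end date, disregard of 4.1.2.8 and an assumed cut-off, so it is not an established effect.

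**Conclusion.** The gap in 4.1.2.8 is real: for a known month in an earlier year, the stated rule produces a date the record itself rules out. For such records exposure and the on-treatment window can be too long, by at most 7 days with EOT on schedule, about 35 days after a 28-day hold, and by more if only a death date exists.

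The 4.1.2 rule is an unresolved conflict with 4.1.2.8. Read literally, it would run a stopped, living patient's exposure to cut-off, but it does not affect the safety window.

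Severity is minor. Only partial or missing last-dose dates are affected, and the documents do not say how many there are. It cannot be concluded that the trial's exposure or safety tables are overstated, only that affected records can be. The key secondary response rate on the Full Analysis Set does not use these rules directly.

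**What to change.** - **SAP 4.1.2.8:** apply the end-of-month branch whenever the known year and month together precede the year and month of the earlier of the EOT and death dates. Keep the existing floor at first dose.
- **SAP 4.1.2:** state that 4.1.2.8 governs the last-dose date, or add the EOT date to the dates compared. Cut-off then applies only to patients with neither an EOT page nor a death date.
- Use one derived last-dose date for exposure, dose intensity and the on-treatment window.

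The cost is two lines of SAP text and the matching program change. No new data are needed.
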